13.3.3. IPV Monitoring

- As in [name] completed study of aPS in Kenya, we will use the CDC definition of IPV, which has been adapted from the CDC website below, and can be found at http://www.cdc.gov/ViolencePrevention/intimatepartnerviolence/definitions.html
 - o The term "intimate partner violence" describes physical, sexual, or psychological harm by a current or former partner or spouse. This type of violence can occur among heterosexual or same-sex couples and does not require sexual intimacy. IPV can vary in frequency and severity. It occurs on a continuum, ranging from one hit that may or may not impact the victim to chronic, severe battering.
 - There are four main types of IPV:
 - Physical violence is the intentional use of physical force with the potential for causing death, disability, injury, or harm. Physical violence includes, but is not limited to, scratching; pushing; shoving; throwing; grabbing; biting; choking; shaking; slapping; punching; burning; use of a weapon; and use of restraints or one's body, size, or strength against another person.
 - Sexual violence is defined as the use of physical force to compel a person to engage in a sexual act against his or her will, whether or not the act is completed or abusive sexual contact.
 - Threats of physical or sexual violence use words, gestures, or weapons to communicate the intent to cause death, disability, injury, or physical harm.
 - Psychological/emotional violence involves trauma to the victim caused by acts, threats of acts, or coercive tactics. Psychological/emotional abuse can include, but is not limited to, humiliating the victim, controlling what the victim can and cannot do, withholding information from the victim, deliberately doing something to make the victim feel diminished or embarrassed, isolating the victim from friends and family, and denying the victim access to money or other basic resources.
- When we use the term IPV in this protocol, we are referring to all 4 types of IPV listed above. However, when we use the term physical IPV, we are referring only the first type of IPV, physical violence.
- Identification of IPV during the study: We will collect IPV data on CRFs from all
 participants in the study. Face-to-face interviews to collect this data will be conducted by
 trained study clinicians, counselors, and field workers at the following time points and
 will be accompanied by counseling and referrals for care and/or additional counseling
 as needed:
 - aPS Eligibility Screening: all participants providing written informed consent for the aPS intervention will undergo assessment for IPV to determine aPS eligibility
 - aPS Enrollment Visit for all participants meeting eligibility criteria and consenting to be enrolled

Version 1.1 17 July 2018 Page 53 of 137

- Weekly for the first month after aPS intervention enrolment and as needed if problems arise – enrolled participants categorized as being at moderate risk (per the rating system described below) for IPV
- 6-week Follow-up Visit all participants newly diagnosed with HIV infection in any intervention component of this study
- ART and PrEP cohort visits following the schedules detailed in Appendices 21.4 and 21.5.
- IPV monitoring forms will include instructions to describe in detail any situation reported and the plan developed to resolve the current problem and prevent any future abuse.
- More intensive monitoring will be conducted if a participant expresses concerns or reports any incident.
- Emergency contact numbers for study staff will be provided to all participants who undergo the aPS intervention.
- Prior to study initiation, all clinicians, counselors, and field workers will be trained to
 collect data on IPV, recognize IPV, and provide IPV counseling and referrals. Training
 will be based on training modules that have been created and implemented successfully
 by [name] and her team. This will ensure that we are identifying all participants at
 risk for IPV, collecting accurate data on IPV to inform scale-up of this intervention, and
 addressing the needs of participants with respect to IPV.
- Rating System for IPV: At the aPS Eligibility Screening Visit, participants who provide
 written informed consent for the aPS intervention will be asked several questions to
 determine their eligibility for the aPS intervention component of our study and to
 classify them as at high, moderate, or low risk for IPV.
 - o Participants will be classified as at high risk for IPV if they report a history of IPV within the last 1 month. *These participants will be excluded from the aPS intervention.*
 - Participants will be classified as at moderate risk for IPV if they report 1) history of IPV during their lifetime either from a current or past partner; and/or 2) fear of IPV if they participate in the study. These participants will receive special monitoring as described below.
 - Participants will be classified as at low risk for IPV if they report 1) no history of IPV during their lifetime either from a current or past partner; and 2) no fear of IPV if they participate in the study. These participants will undergo aPS procedures without special monitoring.
- *Mitigation Plan for Risks:* Our mitigation plan includes 1) special monitoring for participants at moderate risk for IPV; 2) formation of a Protocol Safety Review Team to monitor IPV, as described below; 3) stopping rules for the study.
- Special monitoring: Participants at moderate risk for IPV will be eligible for the aPS intervention, but will be monitored by the study team more closely than those at low risk. Special monitoring involves an additional meeting with a counselor or field worker at a mutually agreed upon location 1 week after the aPS intervention to:

Version 1.1 17 July 2018 Page 54 of 137

- interview participants about IPV
- provide individual or couple counseling
- make referrals for additional care/counseling as needed
- schedule additional monitoring visits as needed
- All monitoring visits will be documented and reported by the counselor or field worker
 to the study coordinator at the end of each week. Any episodes of IPV will be reported
 immediately by the study coordinator to the Safety Review Team as described below.
- The decision to schedule additional follow-up visits after 1 week (or after a shorter interval) will be made by the research team at the time of the first monitoring visit, by the study coordinator after receiving the field staff weekly report, or by the Safety Review Team at any time.

13.4. Protocol Safety Review Team

- A protocol safety review team to monitor adverse events will be formed and will include the following individuals:
 - o [name], co-PI and protocol chair
 - [name], co-PI and protocol co-chair
 - [name], Program Manager
 - [name], Co-investigator
 - A KEMRI Clinical Trials Unit representative, TBN
 - NIAID Medical Officer
 - KEMRI Community Engagement Officer
 - Study Field Worker, TBN
- The Safety Review Team is responsible for reviewing written reports prepared by the study data manager and distributed by the study coordinator. These will include summaries of baseline data, special monitoring data, and 3-month follow-up data.
- Reports will be distributed and reviewed monthly and the committee will meet via teleconference at least twice annually to discuss any safety issues or concerns.
- Because we expect IPV to be a rare event, any IPV reported by research staff that is
 determined to be related to the intervention will prompt an ad hoc report to be
 distributed and may result in an ad hoc teleconference for the entire committee.
- The Safety Review Team will also be responsible for determining whether the aPS intervention needs to be stopped, as discussed in more detail in the following section.

13.5. Stopping Rules

- The Safety Review Team will also be responsible for stopping the aPS intervention (both standard and enhanced aPS) if this becomes necessary. The following "stopping rules" are proposed to guide the Safety Committee in decision-making:
 - More than 3 episodes of *physical IPV* at a *single study site* may warrant stopping aPS procedures at that study site if the violence is deemed related to this intervention.

- o More than 5 episodes of *physical IPV* in the study overall may warrant stopping aPS procedures at all study sites if the violence is deemed related to this intervention.
- While the Safety Review Team will be discussing every episode of IPV in detail, special
 attention will be given to these 2 scenarios which will trigger discussions about stopping
 the aPS intervention, either in an isolated study site or overall.

13.6. Reporting Requirements

- Information on clinical adverse events, social harms, and IPV will be reported by the PI
 and study coordinator to the Safety Review Team and to the UW, Oxford, and KEMRI
 IRBs.
- Study participants will be instructed to contact the study site staff to report any AEs they
 may experience at any time between enrollment and completion of their participation. In
 the case of a life-threatening event, they will be instructed to seek immediate emergency
 care.
- Study staff will record all AEs on CRFs. Study staff will obtain written permission from the participant to obtain and use records from non-study medical providers to complete any missing data element on a CRF related to an adverse event.
- All participants reporting an untoward medical occurrence will be followed clinically, until the occurrence resolves (returns to baseline) or stabilizes. The Safety Committee will determine AE resolution or stabilization in their best clinical judgment.

13.7. Serious Adverse Events

- Serious adverse events (SAEs) will be defined by the Manual for Expedited Reporting of Adverse Events to DAIDS (Version 2.0, dated January 2010) and include any AE that:
 - Results in death
 - Is life-threatening
 - Results in persistent or significant disability/incapacity
 - Is a congenital anomaly/birth defect
 - Requires inpatient hospitalization or prolongation of existing hospitalization Note: Per ICH SAE definition, hospitalization itself is not an adverse event, but is an outcome of the event. Thus, hospitalization in the absence of an adverse event is not regarded as an AE, and is not subject to expedited reporting.
- Important medical events that may not result in death, be life-threatening, or require
 hospitalization may be considered a serious adverse drug experience when, based upon
 appropriate medical judgment, they may jeopardize the patient or subject and may
 require medical or surgical intervention to prevent one of the outcomes listed above.
- A social impact that is reported to the Safety Review Team will be considered serious if significant social harm occurs (e.g., loss of a job, social ostracism).
- Requirements, definitions and methods for expedited reporting of Adverse Events (AEs) are outlined in Version 2.0 of the DAIDS EAE Manual, which is available on the DAIDS RSC website at http://rsc.tech-res.com/clinical-research-sites/safety-reporting/manual.

- The DAIDS Adverse Experience Reporting System (DAERS), an internet-based reporting
 system, must be used for expedited AE reporting to DAIDS. In the event of system
 outages or technical difficulties, expedited AEs may be submitted using the DAIDS EAE
 Form. This form is available on the DAIDS RSC website at http://rsc.techres.com/clinical-research-sites/safety-reporting/daids/paper-eae-reporting.
- · For questions about DAERS, please contact NIAID CRMS Support at
- [contact]. Please note that site queries may also be sent from within the DAERS application itself.
- For questions about expedited reporting, please contact the DAIDS RSC Safety Office at ([contact]).

13.8. Adverse Event Relationship to Study Procedures

- The relationship of all AEs to study procedures will be assessed per the Manual for Expedited Reporting of Adverse Events to DAIDS (Version 2.0, dated January 2010) and clinical judgment. Per the Manual for Expedited Reporting of Adverse Events to DAIDS (Version 2.0, dated January 2010), the relationship categories that will be used for this study are:
 - Related: There is a reasonable possibility that the AE may be related to the study procedures
 - Not related: There is not a reasonable possibility that the AE is related to the study procedures

13.9. Grading Severity of Events

• The Division of AIDS Table for Grading the Severity of Adult and Pediatric Adverse Events (Corrected Version 2.1, July 2017) will be used.

13.10. EAE Reporting Period

- The AE reporting period for this study is defined as the entire study duration for an individual participant (from study enrollment until the participant's final study contact (Follow-Up Phone Assessment Visit/Termination Visit).
- After the protocol-defined AE reporting period, unless otherwise noted, only suspected unexpected serious adverse reactions will be reported to DAIDS if the study staff become aware of the events on a passive basis (from publicly available information).

Version 1.1 17 July 2018 Page 57 of 137

14. SAMPLE SIZE CONSIDERATIONS

The proposed work is powered for the stepped wedge design (Figure 2). Based on our pilot work, we estimate that 50%-60% of adults aged 18-39 at the six participating facilities will be eligible for the study and approximately 50%-80% of these will accept study participation. Our preliminary data shows that approximately 2% of young adults in this age range are diagnosed with prevalent HIV-1 infection under standard care, while approximately 5% will be newly diagnosed with acute (1%) or prevalent (4%) HIV-1 infection in the intervention period. If these estimates are correct, with 1,375 subjects in the observation period and 1,500 subjects in the intervention period and a type I error probability of 0.05, assuming a coefficient of variation (k) of 0.25, we will have >90% power to reject the null hypothesis that the HIV diagnosis rates for experimental and control subjects are equal [57]. This power is more than adequate for multivariable analysis related to the testing of this null hypothesis. Because facilities will not have the laboratory capacity to diagnose HIV before seroconversion during the observation period, the base rate of AHI detection is 0, and power to detect AHI during the intervention period is >90% even if AHI prevalence is well below 1%. The table below presents power for a range of coefficients of variation and acute/prevalent HIV prevalence in the intervention period, given our chosen sample size.

Table. Power for Evaluation of Null Hypothesis that HIV Diagnosis Rates are Equal

Diagnosed HIV, Observation Period	Diagnosed HIV, Intervention Period	Kappa	Power
2.0%	5.0%	0.20	94.4%
2.0%	4.3%	0.20	82.2%
2.0%	5.0%	0.25	93.0%
2.0%	4.3%	0.25	80.0%
2.0%	5.0%	0.30	91.4%
2.0%	4.3%	0.30	77.3%
2.0%	5.0%	0.35	89.4%
2.0%	4.3%	0.35	74.6%

Accounting for correlation within sites (i.e., facilities participating in the randomized trial), precision for the estimated rate of AHI detection is ±0.54%, assuming a prevalence of 1% and k=0.25; if AHI prevalence is 2%, precision will be ±0.81%. For the evaluation of impact and cost-effectiveness, precision is more important than power, since estimates will be used as ranges for modelling. Assuming 150 partners tested as a result of the aPS intervention, we can estimate their HIV prevalence with reasonable precision (binomial confidence limits [CL], 39.8%–56.3%, for 48.0% prevalence); in addition, we will have 80% power to detect a relative risk (RR) of 1.58 or higher for HIV infection in the partners of AHI patients (n=30), compared to partners of prevalent HIV patients (n=120). Assuming 75 new HIV diagnoses from the HIV-1 RNA testing intervention to detect acute and prevalent HIV infection, we can estimate the proportion attaining virologic suppression with reasonable precision (binomial CL, 69.2%–88.3% if 80.0% achieve suppression by month 12); we will have 80% power to detect an RR of 2.84 or higher for failure to suppress among AHI patients (n=15) compared to prevalent HIV patients (n=60).

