Version 1.1 17 July 2018 Page 11 of 137

Secondary Objectives:

- Linkage to care: To determine the feasibility, acceptability, and uptake of offering immediate linkage and treatment to all newly diagnosed HIV-infected patients in the intervention period, comparing this approach to standard care.
- Partner testing: To determine the feasibility, acceptability, and uptake of aPS for partner identification and testing, comparing enhanced aPS with HIV-1 RNA testing in the intervention period to passive referral followed by delayed aPS with standard HIV testing in the observation period.
- Impact and cost-effectiveness: To model the potential impact of
 the HIV-1 RNA testing, linkage, immediate treatment, and aPS
 interventions on the Kenyan HIV epidemic, in terms of
 incremental costs per HIV infection averted, death averted, and
 disability-adjusted life-year (DALY) averted, using data on
 standard care outcomes from the observation period and data
 on intervention outcomes from the intervention period.

Exploratory Objectives:

- Barriers and facilitators: To conduct qualitative in-depth interviews with up to 60 newly diagnosed prevalent and AHI patients and seronegative partners in discordant relationships to gain insights into intervention uptake, including barriers and facilitators to ART or PrEP uptake and adherence in these groups.
- Staff views: To conduct interviews or focus groups with up to 60 individuals who work in the 6 health facilities where the trial will take place (up to 10 participants per facility), to obtain their views on HIV-1 RNA testing and the research carried out at the facility, including challenges to intervention scale-up.

Endpoints:

Primary Endpoints:

HIV-1 RNA testing intervention: Proportion of participants with the following outcomes in the observation and intervention periods:

- tested for HIV infection;
- newly diagnosed with prevalent HIV; and
- newly diagnosed with AHI (0 in the observation period).

Secondary Endpoints:

Linkage to care: Proportion of newly diagnosed patients with the following outcomes in the observation and intervention periods:

- successfully linked to care by week 6; and
- initiating ART by week 6 following HIV diagnosis.

Version 1.1 17 July 2018 Page 12 of 137

For ART cohort participants (intervention period only) we will also assess:

- proportion initiating ART by month 3 following HIV diagnosis;

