- proportion with viral suppression (<1,000 copies/mL) by month 6 and month 12 following ART initiation.

Partner testing: For newly diagnosed individuals with acute or prevalent HIV, we will also compare the following week 6 outcomes between the observation and intervention periods:

- number of partners reported;
- number of partners successfully contacted;
- number of partners tested;
- number of partners newly diagnosed with prevalent HIV infection;
- number of partners newly diagnosed with AHI (0 in the observation period);
- number of HIV-infected partners newly engaged in care; and
- number of HIV-uninfected partners initiating PrEP.

For PrEP cohort participants (intervention period only) we will also assess:

- proportion initiating PrEP by month 3 following cohort enrollment;
- proportion with adherence >80%, measured by self-report or MEMS® cap at months 3 and 6 following PrEP initiation.

Impact and cost-effectiveness: Model outputs will include the following:

- HIV infections averted
- Deaths averted
- Disability-adjusted life-years (DALY) averted
- Costs per HIV infections averted
- Costs per death averted
- Costs per DALY averted

Impact and cost-effectiveness will be evaluated by comparing these outputs for standard care (observation period) to these outputs for the HIV-1 RNA testing intervention (intervention period).

Barriers and facilitators: Qualitative results will present barriers and facilitators to the following components:

- HIV testing uptake
- aPS uptake
- ART uptake
- ART adherence
- PrEP uptake
- PrEP adherence

Version 1.1 17 July 2018 Page 13 of 137

Novel HIV-1 RNA testing intervention to detect acute and prevalent HIV infection – Tambua Mapema Plus

Staff views: Qualitative results will present staff views on the detection of AHI and the research carried out at the HIV-1 RNA testing intervention facilities, including challenges to intervention scale-up.

Version 1.1 17 July 2018 Page 14 of 137

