In the **intervention period**, there are four major interventions being tested: testing for acute and prevalent HIV infection, aPS using our HIV-1 RNA testing intervention (i.e., enhanced aPS), an ART cohort at KEMRI, and a PrEP cohort at KEMRI. Again, adults seeking care at primary care clinics with no history of HIV and a risk score of 2 or more will be offered enrollment. In the intervention phase, all participants will undergo HIV testing consisting of testing for HIV-1 RNA initially, followed (if positive) by testing with 2 rapid HIV tests per Kenyan HIV testing guidelines. Those who test negative end participation at the baseline visit after the CASI/CAPI as above. Those who test positive (either AHI or prevalent case, estimated to be about 5% for this combined outcome) are offered enhanced aPS and participation in the ART cohort at KEMRI and can accept or decline each one. Those who decline follow-up at KEMRI will end their participation at the 6-week visit (as described above for the observation period), those who accept will be followed at KEMRI for 12 months. Those who test positive will also be offered participation in qualitative interviews, which they may accept or decline without influencing other components.

[figure not shown]
Partners of observation phase HIV-positive participants (i.e., index cases with prevalent HIV infection) will be offered referrals for risk reduction counseling and for HIV care, if infected. Partners of intervention phase HIV-infected participants (i.e., index cases with newly diagnosed acute and prevalent HIV infection) will be offered the HIV-1 RNA testing intervention (as described for participants in the intervention phase above) and enrollment into the KEMRI ART cohort or PrEP cohort based on their test results. If they accept either cohort, they will be followed for 12 months. If they decline and are HIV positive, their participation will end after a 6 week visit as above. If they decline and are HIV negative, their participation will end at the baseline visit after the CASI/CAPI as above. In the intervention period, partners newly diagnosed with HIV through the enhanced aPS intervention will also be offered the enhanced aPS intervention to identify and test their partners. Identified partners of these individuals will be offered the same options as partners of index cases diagnosed in the stepped wedge trial.

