15.2. Linkage to Care

During the intervention period, participants with newly diagnosed HIV infection will be offered referral to our research clinic, and enrolled in ongoing HIV care cohorts. We will evaluate the following outcomes for prevalent HIV, acute HIV, and the combined outcome (acute or prevalent HIV infection): (1) proportion successfully linked to care by week 6; (2) proportion initiating ART by week 6 and month 3 following HIV diagnosis; (3) proportion with viral suppression (<1,000 copies/mL) by month 6 and month 12 following ART initiation. All proportions will be calculated with exact binomial CI, assuming independence between individuals. We will compare these outcomes between prevalent HIV and AHI cases using Pearson Chi square or Fisher exact tests, as appropriate. We will also compare these proportions to outcomes in HIV-infected partners using the same methods. As above, in analyses in which multiple null hypotheses are tested, p values will be adjusted using the Holm–Bonferroni method.

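### Section 14's suppression precision and its 80% power at a relative risk of 2.84 treat all 75 expected diagnoses as evaluable, a best case, and the power figure is a normal approximation that Fisher's exact test does not reach

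*Combined protocol and SAP*

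**What the plan says.** Section 14 sets the basis as "Assuming 75 new HIV diagnoses from the HIV-1 RNA testing intervention" and gives two figures on it. The first is a precision statement, "binomial CL, 69.2%–88.3% if 80.0% achieve suppression by month 12". The second is a power statement, "we will have 80% power to detect an RR of 2.84 or higher for failure to suppress among AHI patients (n=15"), set against 60 prevalent cases.

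The endpoint is defined more narrowly. The Protocol Summary places it under the lead-in "For ART cohort participants (intervention period only) we will also assess" and words it as "proportion with viral suppression (<1,000 copies/mL) by month 6 and month 12 following ART initiation".

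Cohort membership is voluntary. Section 8 lets a newly diagnosed patient accept or refuse it, and adds: "Those who decline follow-up at KEMRI will end their participation at the 6-week visit". Section 17.4 provides for people who want to postpone ART, and section 11.7 allows withdrawal at any time.

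For the analysis, section 15.2 plans exact binomial confidence intervals and states: "We will compare these outcomes between prevalent HIV and AHI cases using Pearson Chi square or Fisher exact tests, as appropriate". It gives no rule for choosing between the two tests. It compares infected partners with these patients as a separate step.

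**The concern.** A patient contributes to the month-12 suppression result only after joining the cohort, starting ART and having a viral load measured at that time. Section 14 counts every diagnosis, so both figures assume that all three steps happen for everyone. It neither states that assumption nor allows for any loss.

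The power figure raises a second question. With 15 acute cases and a failure rate near 20%, expected cell counts are small. Section 15.2 names a test for that situation, and it has less power than a normal approximation suggests.

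What is at stake is how a non-significant acute-versus-prevalent comparison would be read. A reader who takes the 80% at face value could treat such a result as fairly strong evidence against a near-threefold difference in failure.

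**Working it through.** **Inputs**
- Group sizes 15 acute and 60 prevalent, total 75; suppression 80%, so failure 20%; relative risk 2.84 (all section 14).
- Type I error 0.05 (section 14, given there for the primary comparison); two-sided is assumed here.
- Evaluable fractions below 100%: assumed, because the documents give none.

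**1. Reproduce the interval.** Clopper-Pearson for 60/75 gives 69.17% to 88.35%, which matches the stated limits within rounding. The Wald interval is 70.9% to 89.0% and Wilson 69.6% to 87.5%; neither matches. The method is therefore the exact one planned in section 15.2.

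**2. Reproduce the power.** Take 20% failure in the prevalent group, so failure in the acute group is 2.84 × 0.20 = 0.568.
- Pooled rate: (15 × 0.568 + 60 × 0.20)/75 = 0.2736.
- Null standard error: √[0.2736 × 0.7264 × (1/15 + 1/60)] = 0.1287.
- Alternative standard error: √[0.568 × 0.432/15 + 0.20 × 0.80/60] = 0.1379.
- z = (0.368 − 1.96 × 0.1287)/0.1379 = 0.839, so power is 79.9%. Solving for 80% gives a relative risk of 2.842.

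Other common formulas do not match: 70.4% with continuity correction, 76.1% unpooled, 77.1% arcsine, 86.1% on the log relative risk. The stated 80% is the uncorrected pooled normal approximation.

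**3. Which test applies.** The smallest expected count is 15 × 0.20 = 3.0 if both groups fail at 20%, and 15 × 0.2736 = 4.1 at a relative risk of 2.84. Both are below 5, where Fisher's test is the conventional choice.

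**4. Exact power.** Enumerate every outcome of two independent binomials and sum the probability of those with p ≤ 0.05. The interval is Clopper-Pearson at 80% suppression.

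| Evaluable (acute / prevalent) | Fisher power at 2.84 | Pearson power at 2.84 | Relative risk for 80% Fisher power | Exact interval |
|---|---|---|---|---|
| 15 / 60 (all 75) | 75.8% | 80.4% | 2.94 | 69.2–88.4% |
| 12 / 48 (assumed, 60 of 75) | 63.3% | 72.1% | 3.23 | 67.7–89.2% |
| 10 / 40 (assumed, 50 of 75) | 58.7% | 63.2% | 3.40 | 66.3–90.0% |

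A smaller assumed loss, 14 versus 56, gives 72.0% by Fisher and 79.3% by Pearson. (The first row's upper limit is 88.35%; section 14 prints 88.3%.)

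**The case against.** The basis of 75 is stated openly, and the consent table in section 17.3 plans the same number for the ART cohort, plus an unknown number of infected partners. That stands as to transparency. It does not make 75 the evaluable number, because the endpoint conditions still apply and section 15.2 compares partners separately.

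The plan does not prescribe Fisher's test. Pearson's test evaluated exactly keeps 80.4% power at 15 versus 60, with an actual type I error of 0.0499 when both groups fail at 20%. This stands: with complete follow-up the stated 80% is right for one of the two named tests, and Fisher is an inference from the usual expected-count rule. With all 75 evaluable, the choice of test costs about 4 points (80% against 75.8%).

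The larger drops rest on assumed losses. This also stands. They are illustrations, and part of each Fisher figure comes from the test itself.

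Three stronger readings are tempting, and the documents do not support them:
- A reader might infer that the interval is also a normal approximation. It reproduces as Clopper-Pearson, the planned method.
- A reader might infer that true power will be about 60%. No uptake, deferral or retention rate is given from which to derive that.
- A reader might infer that suppression must also be analysed with all diagnosed patients as the denominator. Section 11.3 refers those who decline the cohort to other ART programmes, where they may be suppressed. Counting them as not known suppressed would define a different, debatable endpoint.

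**Conclusion.** The point holds as a should-fix correction to a stated power. Section 14's two suppression figures are best cases, because they need full cohort uptake, full ART initiation and a month-12 viral load from everyone. The interval's method is correct, and the interval widens only modestly with loss. The 80% power is a normal approximation: with nobody lost it is 75.8% by Fisher and 80.4% by Pearson, and once patients are lost both fall below 80% in every case examined.

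The results assume two-sided 0.05 and 20% failure in the prevalent group, which is the reading that reproduces the plan's figure. They include no Holm–Bonferroni adjustment; section 15.2 applies one where several hypotheses are tested, and it could lower power further. The comparison is secondary, and the sample size rests on the stepped wedge comparison, so the primary power is untouched.

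**What to change.** In section 14:
- Label 75 (15 and 60) as the maximum evaluable number.
- State which of the two tests the power refers to and calculate it exactly. By Fisher, that is about 76% at a relative risk of 2.84, or 80% at about 2.94.
- Add a sensitivity range marked as assumed, for example 60 and 50 of 75 evaluable: 80% Fisher power at relative risks of about 3.2 and 3.4, with intervals of 67.7–89.2% and 66.3–90.0%.

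The interval method needs no change, and no additional analysis is required.

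The cost is a few lines of text and less favourable figures. Enrolment, procedures and the primary analysis stay as they are.
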